1.3 Clinical Data to Date

Senescent cell clearance from humans: In the first clinical study published about senolytics, a

pilot, open-label study in 14 patients with IPF, we found that 9 pulse-doses of oral D+Q over 3 weeks led to improved 6-minute walk distance, walking speed, ability to rise from a chair, and short physical performance battery by 5 days after the final dose¹¹⁹. These results led to initiation of a Phase IIb randomized, placebo-controlled, double-blind trial that is currently underway.

Interim results of a Phase 1, open-label, clinical trial of D+Q for subjects with diabetic kidney disease (DKD) underway at Mayo (ClinicalTrials.gov Identifier: NCT02848131) showed a 3 day oral course of D+Q administered as pulse doses in 9 subjects with DKD reduced adipose tissue senescent cell burden assayed by p16^{INK4a+} and SA-βGal⁺ cells by 11 days after the last dose, compared to biopsies before D+Q administration⁷⁶. A composite score of 10 circulating SASP factors was significantly decreased 11 days after completing the 3 day D+Q intervention. Furthermore, activated CD68⁺ macrophage tissue infiltration was significantly decreased. This trial is continuing (goal=30) to test effects of senolytics on adipose tissue and skin senescent cell abundance and urine SASP factors, metabolic and renal function, inflammation, quality of life, safety (drug toxicity), and tolerability. No serious drug side effects have emerged so far. Evidence continues to show clearance of senescent cells. Each subject will be followed for 4 months after the single course of D+Q to provide data for a larger Phase IIb randomized, placebo-controlled, double-blind trial of senolytics for DKD.

The senolytic drug to be used in our study here is Fisetin. We found that frailty in elderly women is associated with senescent cell burden and the associated inflammation in adipose tissue biopsies⁹⁸. Furthermore, senolytics alleviated frailty in the subjects in our IPF trial¹²⁰. Therefore, a Phase IIb double-blind, placebo-controlled clinical trial of Fisetin to reduce senescent cell burden and alleviate frailty and inflammation, AFFIRM, has commenced. Oral Fisetin 20 mg/kg/day for 2 days *vs.* placebo is being administered as daily pulsed doses for frailty (gait speed <0.8 m/sec) and inflammation in elderly women with multi-morbidity. This trial at Mayo Clinic is FDA-approved (ClinicalTrials.gov Identifier: NCT03430037) and has enrolled over 20 subjects who have received Fisetin or placebo. The trial is not yet unblinded. No participants have had severe or serious adverse events so far at the same doses of Fisetin as proposed here for the same indications, clearing senescent cells and alleviating physical dysfunction and inflammation (in CoV patients).

1.4 Dose Rationale

Others have treated mice with Fisetin 50 mg/kg/day for weeks without evidence of toxicity ¹²¹. We treated 4 male and 4 female 8 month old C57/Bl6 mice with Fisetin 500 mg/kg/day (25-fold higher than the dose to be used in this clinical trial) by oral gavage for 2 consecutive days compared to 4 male and 4 female mice treated with vehicle. We found no evidence of substantial toxicity, as assessed by monitoring activity, food intake, and respiratory quotient in metabolic cages (Comprehensive Laboratory Animal Monitoring System, Columbus Instruments) for 48 hours after the last Fisetin dose. We administered 100 mg/kg/day for 2 consecutive days by mouth as daily pulse doses, 5 times the dose proposed in in this clinical trial, to 2 older *Rhesus* monkeys (ages 19 and 28 years, which is old for this species) at the National Primate Center. In over 1 month of close monitoring, neither monkey had adverse effects such as reduced appetite, altered activity, vomiting, or diarrhea. Acknowledging the higher rates of drug metabolism in mice compared to humans and differences in physiology between non-human primates and humans, in an effort to avoid side effects, a daily dose of ~20 mg/kg was selected here. We verified that this dose is sufficient to reduce senescent cell burden in mice. Our studies in very old coronavirus-infected mice demonstrated that this dose of Fisetin dramatically enhances survival (Figs. 18, 20, and 22).

1.5 Risks and Benefits

There are appear few if any risks of Fisetin at the doses to be used that we have evidence for, provided the subjects meet the exclusion criteria in the protocol regarding medications that Fisetin could interfere with. We have not seen serious or severe adverse events so far in elderly frail women enrolled in our AFFIRM studies from Fisetin 20 mg/ kg/ day for 2 consecutive days in the over 20 subjects randomized to Fisetin or placebo. We did not see adverse effects such as altered food intake, weight, or behavior in old *Rhesus* macaques given 5 times the dose proposed here or in mice given 25 times the dose.

Based on our studies in mice, there may be decreased morbidity and mortality due to β -coronavirus infection after Fisetin administration. All subjects in this study will be elderly (and/or chronically-ill) and hospitalized with mild or moderate CoV infection that could progress to severe or critical disease. The potential benefit to individual subjects in this trial and other people might be large.

In this study, we will examine the effect of oral/ enteral Fisetin as a senolytic agent in humans, which may have immense potential for and reducing frailty/ physical dysfunction and inflammation and alleviating morbidity and mortality from CoV or other infections in older subjects and those with other conditions and diseases associated with accumulation of senescent cells. As an additional, advantageous, off-target effect, removal of senescent cells may allow for functional improvement of neighboring or distant tissues and cells, including MSC's, accelerating recovery. We found that senolytics restore function of MSC's^{20,73}. Our collaborator, [name], working with investigators in China, noted that transplanting normal MSC's can alleviate symptoms and signs in severely ill CoV-infected patients¹²². Thus, an additional benefit of senolytics for CoV could be alleviation of stem cell and progenitor dysfunction.

Based upon review of the published literature and our pre-clinical data, we do not anticipate the occurrence of serious adverse events with the prescribed regimen in this study. We have identified a variety of drug-drug interactions (*e.g.*, current use of warfarin) for which we established exclusion criteria or modification plans to minimize associated risks. We could find no reports of Fisetin toxicity in the literature. Some flavonols have been associated with DNA damage *in vitro*, but Fisetin exerts little or no genotoxic effects⁶⁰. To the contrary, Fisetin has been noted to be anticarcinogenic^{48,61,62}. Indeed, we found that chronic Fisetin administration delays cancer in mice and increases remaining lifespan in old mice as well as DNA damage/ genotoxicity highly-prone *Ercc1*^{-/Δ} mice by over 17%⁶³. Since up to 50% of most mouse strains die from cancers, this shows that the beneficial effects of Fisetin on such pro-carcinogenic factors as senescent cell burden and tissue chronic inflammation appear to more than counteract any theoretical effects of flavonol-associated genotoxicity. **Fisetin actually reduces cancer risk**, as opposed to increasing it, as would be expected if Fisetin-induced DNA damage were a risk for the subjects in the clinical study proposed here.

Overall, we do not anticipate substantial risk from the natural product, Fisetin, which is present in many foods, including cucumbers, strawberries, and other fruits and vegetables, albeit at levels lower than those that will be used here. Thus, the risks of using this drug are likely minimal compared to the anticipated benefits for patients with CoV infection severe enough to require hospitalization and the knowledge that may be gained from these clinical investigations.

2 STUDY OBJECTIVES

The primary objective of this study is to determine whether short-term treatment with Fisetin reduces

the rate of complications related to COVID-19 (CoV) disease using a 7 point score adapted from the WHO Ordinal Scale for Clinical Improvement of CoV (Appendix A). The secondary objective is to determine safety and tolerability of treatment with Fisetin in this patient population. Exploratory objectives are to evaluate links between soluble and genetic markers of senescent cell abundance, SASP factors, inflammation, viral load, and treatment effects.

3 STUDY DESIGN

This will be an enterprise wide, randomized, double-blind, placebo-controlled study. Following signature of the informed consent form, approximately 150 subjects meeting all inclusion and no exclusion criteria will be randomized to receive either Fisetin or placebo (1:1 allocation ratio) for days 0 and 1 AND days 8 and 9. Follow-up phone assessments will occur at 15, 30, and 60 days following randomization for evaluation of the occurrence of any trial endpoints or other adverse events. Exploratory objectives are to evaluate links between soluble and genetic markers of senescent cell abundance, SASP factors, inflammation, viral load, and treatment effects and if Fisetin treatment during acute CoV infection decreases Long-hauler syndrome at Days 60.

3.1 Study Schedule

The schedule of visits for this study is outlined in Table 1. However, a patient may be evaluated at any time for safety concerns.

3.2 Enrollment

Informed consent will be obtained from patients who volunteer to participate in the study prior to the conduct of any study-specific procedures. The patient will be considered "enrolled" into the study at the time an informed consent is provided.

Biomarker samples collection including senescent biomarker analysis will be optional for participants. The informed consent form will reflect this option and patients will specifically be asked to consent to this biomarker evaluation.

3.3 Screening Evaluations and Randomization

Screening evaluations will include a review of the patient's medical history and assessment of concomitant medications to determine if the patient qualifies for the study. Patients who meet all inclusion criteria and no exclusion criteria will be randomized to receive the study drug or placebo. All patients must be randomized within 10 days of the diagnosis of COVID-19 infection.

Women of childbearing potential must have a negative urine pregnancy test result after the time of randomization, but before IP administration in order to qualify. Qualifying patients will be randomized to receive placebo or fisetin administered in a blinded manner. Blinded randomization will be performed through an automated Interactive Web Response System (IWRS). 75 patients will be randomized to active treatment and 75 patients will be randomized to placebo for a total of 150 randomized patients.

3.4 Active Treatment Period

All patients will receive study medication dosing (either Fisetin 100 mg or matching placebo) (PO) ON day 0 and 1 And Day 8 and 9. If a dose is missed, it should not be replaced. Throughout the study, patients will undergo phone visits (at 15, 30, and 60 days) to assess for potential study endpoints and other adverse events (AEs). Patients will be dispensed the entire supply of study medication on Day 0 to use for the duration of the study.

At each phone contact, patients will be:

- 1) questioned in a non-specific manner for the occurrence of AEs and any change in concomitant medications
- 2) 7 point score adapted from the WHO Ordinal Scale for Clinical Improvement of CoV.

Fecal, urine and buccal swab samples for biomarker are optional for the participants. The informed consent form will reflect this option and patients will specifically be asked to consent to this biomarker evaluation.

Please refer to Table 1 and Appendix A for Timetable of Visits and Requirements.

COVFIS-HOME: COVID-19 PILOT STUDY OF FISETIN TO ALLEVIATE DYSFUNCTION AND DECREASE COMPLICATIONS Version 4.0, 18NOV2021

Table 1 Timetable of Visits and Requirements

Visits	1 Screening/Ra ndomization Phone call	2 ^a Randomization/ Baseline Phone call		3 ^b Phone contact		4b Phone contact	5 ^b Phone contact	6 ^b Phone contact
Days		0	1	8 (-/+ 2 days ^d)	9	15 (-/+ 2 days)	30 (-2/+7 days)	60 (-/+ 14 days)
Informed consent	X					· · ·	V	• /
Medical/Surgical history	X							
Review Concomitant Medications	X	X		X		X	X	X
Phone contact	X	X		X		X	X	X
Review Inclusion/Exclusion criteria	X	X						
Urine pregnancy test (only women of childbearing potential)		X		X				
Randomization		X						
SF-36 Health Survey		X		X		X	X	X
Buccal, fecal and urine sample for biomarkers (optional)		X				X	X	Х
Record potential study endpoints (ordinal scale)		X		X		X	X	X
Review Adverse Events		X		X		X	X	X
Study medication dispensing		X						
Study medication dosing		X	X	X	X			

a) Screening Visit 1 and Visit 2 may be performed on the same day; under these circumstances, requirements at both Screening Visit 1 and Visit 2 will be performed once.

b) Phone contact

c) Saliva sample for pharmacogenomics evaluation will be collected using saliva collection kit.

d) Phone contact can occur + or - 2 days; however study drug administration should still occur on days 8 and 9.

4 STUDY POPULATION

4.1 Source and Number of Patients

A total of 150 patients will be randomized.

4.2 Patient Selection Criteria

4.2.1 Inclusion Criteria:

All of these criteria must be met:

- Males and females, at least 18 years of age, capable and willing to provide informed consent;
- Patient must have received a diagnosis of COVID-19 infection within the last 10 days;
- Outpatient setting (not currently hospitalized or under immediate consideration for hospitalization);
- Patient must possess at least one of the following high-risk criteria: 70 years or more of age, obesity (BMI ≥30 kg/m²), diabetes mellitus, immune deficient state (primary or secondary immunodeficiency), history of hypertension (systolic blood pressure ≥150 mm Hg), known respiratory disease (including asthma or chronic obstructive pulmonary disease, current or previous smoking), known heart failure, known coronary disease, fever of ≥38.4°C within the last 72 hours, dyspnea at the time of presentation, bicytopenia, pancytopenia, or the combination of high neutrophil count and low lymphocyte count;
- Female patient is either not of childbearing potential, defined as postmenopausal for at least 1 year or surgically sterile, or is of childbearing potential and practicing at least one method of contraception and preferably two complementary forms of contraception including a barrier method (e.g. male or female condoms, spermicides, sponges, foams, jellies, diaphragm, intrauterine device (IUD)) throughout the study and for 30 days after study completion;
- Patient must be able and willing to comply with the requirements of this study protocol.

4.2.2 Exclusion Criteria:

None of these exclusion criteria should be met:

- Patient currently hospitalized or under immediate consideration for hospitalization;
- Patient currently in shock or with hemodynamic instability;
- Patient with severe hepatic disease (as *per* clinical judgement) or liver enzymes >2x the upper limit of normal;
- Female patient who is pregnant, breast-feeding, or is considering becoming pregnant during the study or for 1 day after the last dose of study medication;
- Patient currently taking Sirolimus, Tacrolimus, or other mTOR inhibitors for other indications (mainly chronic indications represented by organ transplantation or autoimmune diseases);

- On Warfarin therapy; Subjects taking any of the medications listed in Appendix C may participate if they are otherwise eligible AND the medication can be safely held during the following times:
 - o Immediately before the 1st IP administration (Day 0) until at least 10 hours after the 2nd IP administration (Day 1)
 - o Immediately before the 3rd IP administration (Day 8) until at least 10 hours after the 4th IP administration (Day 9)
- Patient with a history of an allergic reaction or significant sensitivity to Fisetin;
- Patient undergoing chemotherapy for cancer;
- Patient is considered by the investigator, for any reason, to be an unsuitable study candidate.
- History of diverticulitis or diverticulosis with GI bleeding, as per clinical judegement.

4.3 Prohibited, Allowable, and Concurrent Medications

The use of concomitant medications at the time of randomization will be recorded in the eCRF (with the exceptions of concomitant medication taken "when necessary" (PRN)).

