From proteomic/transcriptomic databases and using bio-informatics methods, we discovered the SCAP network⁴³. Through RNA interference analyses, we demonstrated that transiently disabling this SCAP network leads to apoptosis of senescent cells, while normal cells without a SASP are not affected, the "Achilles' heel" of senescent cells. We next used bioinformatics approaches to identify drugs and natural products that act on critical SCAP nodes. Among these are Fisetin, Quercetin (Q), Dasatinib (D), and now over 20 others. We found these agents selectively eliminate senescent cells in mice and humans. They alleviate multiple conditions in mice, including diabetes and its complications, cardiovascular disorders (including heart failure and vascular dysfunction), dementias, pulmonary dysfunction (including bleomycin-induced lung disease), diabetes and its complications, frailty, kidney and liver damage or dysfunction, osteoporosis, osteoarthritis, and delay cancer and extend healthspan and lifespan^{5,21-24}.

We intentionally selected drugs for further development from among those identified as being senolytic. We focused on drugs that: 1) were already FDA-approved or were natural products with a history of safe human use, 2) could be administered orally, and 3) have a short elimination half-life ($T\frac{1}{2}$). Fisetin met these criteria. It is a natural product with a favorable safety profile, is effective orally, and has an elimination $T\frac{1}{2} \sim 3$ hours, meaning it is cleared within a half day.

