1.1 Investigational Product (IP)

An IP is defined as a pharmaceutical form of an active substance or placebo being tested or used as a reference in a clinical study, including products already with a marketing authorization but used or assembled (formulated or packaged) differently than the authorized form, or used for an unauthorized indication, or when used to gain further information about the authorized form. The IP will be stored in a secure area according to local regulations. Investigators will have responsibility for ensuring that IP is only dispensed to study subjects. The IP (Fisetin and placebo) will be dispensed only by authorized personnel according to regulations that apply at Mayo Clinic Rochester. In this protocol, the IP are Fisetin and placebo.

Fisetin: Fisetin is a member of the flavonoid family, a family of naturally-occurring polyphenolic compounds. As a natural product, it is widely sold, including by Amazon, from which it is available in containers of 30 capsules of 100 mg Fisetin/ capsule at <\$20 per container. The structure of Fisetin is similar to that of Q, which is one of the first two senolytic drugs discovered (Fig. 6). Fisetin, a high Trolox-equivalent antioxidant, is present in many fruits and vegetables such as apples, persimmon, grapes, onions, and cucumbers, with the highest concentration found in strawberries ($160 \mu g/g$)^{48,49} (Fig. 7). The average dietary intake of naturally-occurring Fisetin was approximately 0.8 mg/day in an earlier Japanese study^{50,51}. However, the average total intake of polyphenols, comprised mainly of flavonoids, is around 1 gram per day, although it may be quite variable (52-54). Fisetin has little or no odor or taste.

Fig. 6. Structure of the senolytic flavonol, Q.

Quercetin, one of the first two senolytic drugs identified (along with Dasatinib [D]), and which is present in apple peels, has a bitter taste and is less bioavailable and has a longer elimination T½ than Fisetin.

Fig. 7. Structure of Fisetin. Fisetin differs from Q by an hydroxyl group. It has little or no odor or taste. Its terminal $T\frac{1}{2}$ in mice is ~ 3.1 hrs¹. This short half-life makes Fisetin ideal as a senolytic drug to ablate pro-inflammatory, pro-apoptotic, non-dividing senescent cells in a "hit-and-run" fashion⁵.

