Due to its being a hydrophobic compound, Fisetin easily penetrates cell membranes, entering into cells to exert antioxidative and other effects^{55,56}. Other promising biological activities include anti-hyperlipidemic⁵⁶⁻⁵⁸, anti-inflammatory⁵⁷, neurotrophic, apoptotic⁵⁹, and antiproliferative effects³⁶.

There are reports of genotoxicity due to some flavonols, but Fisetin may exert little or no genotoxic effects *in vivo*⁶⁰. Indeed, Fisetin has been noted to be anticarcinogenic^{48,61,62}. We found that chronic Fisetin administration delays cancer in mice and increases remaining lifespan in old mice by over 17%⁶³. Since up to 50% of most mouse strains die from cancers, this suggests that the beneficial effects of Fisetin on such pro-carcinogenic factors as senescent cell burden and tissue chronic inflammation appear to more than counteract any theoretical effects of flavonol-associated genotoxicity. In the same mouse study, Fisetin was administered to a murine model of a human progeroid syndrome⁶³. These mice are profoundly sensitive to genotoxic agents⁶⁴, yet their health and lifespan were improved by long-term, high dose Fisetin⁶³.

Fisetin is available as a dietary supplement. Other flavonols such as Q have been safely used in clinical trials in amounts up to 500 mg twice daily for up to 8 weeks. To date, no reports of significant toxicity for Fisetin *in vivo* have been made. Since Fisetin along with other flavones and flavonoids, has been shown to inhibit cytochrome P450 2C9, CYP3A4, and others (Section 3.9.4), precaution will be taken to avoid significant drug-drug interactions, *e.g.*, with warfarin⁶⁵.

We demonstrated that Fisetin is a senolytic agent and alleviates multiple senescence-associated disorders in mice, decreases physical dysfunction if administered to old mice, attenuates age-related tissue damage and pathology, and extends remaining lifespan by 17%^{44,63}. We have not found any adverse effects in mice (at up to 25 times the dose used in the mouse effectiveness studies [below] or the dose for humans proposed here), old *Rhesus* monkeys (at up to 5 times the dose for humans proposed here), or humans so far. We obtained a full IND for Fisetin from the FDA and have a GMP drug supply handled by Mayo Research Pharmacy.

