Fisetin 100 mg capsules or Fisetin (with cellulose) powder (in water, other chilled or room-temperature drinks, apple sauce, pudding, yogurt, or enteral hydration/ nutrition solutions) will be administered orally for 2 consecutive days on study Days 0 and 1. To reduce senescent cell abundance by a "hit-and-run" approach, the full daily doses of Fisetin will be administered within 30 minutes. The investigational supplies will be obtained from Vital Nutrients, a contracted GMP manufacturer. Fisetin capsules supplied by Vital Nutrients are opaque blue in color. Fisetin powder is a green yellow color. We established stability parameters for Fisetin in collaboration with Mayo Clinic's Department of Laboratory Medicine and Pathology. We acquired an IND for Fisetin after establishing botanical sourcing, GMP isolation by Vital Nutrients, assurance of lack of contaminating pesticides, heavy metals, and solvents, and stability, degradation, and accelerated toxicity testing.

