Appendix C. Excluded Medications and Dosing Modifications

Subjects taking any of the medications listed in Appendix C may participate if they are otherwise eligible AND the medication can be safely held during the following times:

- Immediately before the 1st IP administration (Day 0) until at least 10 hours after the 2nd IP administration (Day 1)
- Immediately before the 3rd IP administration (Day 8) until at least 10 hours after the 4th IP administration (Day 9)

Cardiac:

- Digoxin
- Flecainide
- Amiodarone

Psychiatric:

- Duloxetine (Cymbalta)
- Lithium
- Clozapine (Clozaril)
- Thioridazine (Mellaril or Melleril)

Neurologic:

- Carbamazepine (Tegretol)
- Phenobarbital (Luminal and Solfoton)
- Phenytoin (Dilantin, Phenytoin Sodium, Phenytek)
- Fosphenytoin (Cerebyx)
- Riluzole (Rilutek; Used to treat amyotrophic lateral sclerosis ALS)

Antimicrobial/fungal:

- Aminoglycosides (Eg. amikacin, gentamicin, kanamycin, neomycin, netilmicin, paromomycin, streptomycin, tobramycin)
- Azole antifungals (fluconazole, miconazole, voriconazole) (if absolutely necessary, levels must be subtherapeutic or therapeutic)
- Macrolides (clarithromycin)
- Antivirals (nelfinavir, indinavir, saquinavir)

Oral hypoglycemic/Anti-Diabetes drugs:

- Glimepiride (Amaryl)
- Glyburide (DiaBeta, Glynase PresTab, Micronase)

Anticoagulants/ Antiplatelet:

- Warfarin
- Full dose aspirin

Others:

- Cyclosporine
- Methotrexate
- Nitroglycerin
- St. John's Wort
- Theophylline
- Tyrosine Kinase Inhibitors (list included further down in this appendix)
- Tizanidine (Zanaflex)
- Tacrine

Version 4.0, 18NOV2021

• Diclofenac

Version 4.0, 18NOV2021

Continuation of Excluded Medications

Sensitive Substrates CYP2C9, CYP2C19, CYP1A2, Other (OATP1B1)

	Sensitive substrate	Drugs with a narrow therapeutic
		range
CYP2C9	Glyburide	Fosphenytoin
	Losartan	Phenytoin
		Warfarin
		Glimepiride
		Diclofenac
		Bosentan
CYP2C19		Phenytoin
CYP 1A2	Clozapine	Theophylline
	Olanzapine	Tizanidine
		Warfarin
		Ramelteon
		Tacrine
		Duloxetine
		Mexiletine
		Riluzole
Other	Corticosteroids	
(OATP1B1)	Thyroid hormones	
	Eluxadoline	
	Eltrombopag	
	Pioglitazone (Actos) - monitor blood glucose levels closely or	
	½ dose QD	
	Enzalutamide	
	Colchicine (½ dose QD until 10 hours after the last (2 nd) IP	
	administration	
	Venlafaxine (skip dose on study drug Day 2; then resume as	
	usual)	
	Atorvastatin (QOD or ½ dose QD until 10 hours after the last	

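### Fisetin is sold over the counter at the study's capsule strength, but no rule excludes or bars non-study fisetin or quercetin supplements, so placebo-arm use could dilute the comparison

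*Combined protocol and SAP*

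**What the plan says.** **Availability.** Section 1.1 (Investigational Product) says of fisetin that "it is widely sold, including by Amazon, from which it is available in containers of 30 capsules of 100 mg Fisetin/ capsule", at under $20 per container, and later that "Fisetin is available as a dietary supplement". The study product is given as "Fisetin 100 mg capsules or Fisetin (with cellulose) powder", so the capsule strength is the same.

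**Eligibility.** The only criterion in Section 4.2.2 or the Synopsis that names fisetin is "Patient with a history of an allergic reaction or significant sensitivity to Fisetin". Neither prior nor current use is mentioned.

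**During the trial.** Section 4.3 (Prohibited, Allowable, and Concurrent Medications) is a single sentence: "The use of concomitant medications at the time of randomization will be recorded in the eCRF", with as-needed drugs exempted. It prohibits nothing. Section 3.4 has each phone contact ask, without prompting on specific products, about adverse events and changes in concomitant medication. The visit timetable schedules a medication review at screening and on Days 0, 8, 15, 30 and 60.

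**Other senolytics.** Of the agents that act on the target network, Section 1.1 (Background) says: "Among these are Fisetin, Quercetin (Q), Dasatinib (D), and now over 20 others". Appendix C lists St. John's Wort but neither fisetin nor quercetin. Dasatinib appears in its tyrosine kinase inhibitor table, so users may enter only if the drug can be held around the dosing days.

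**Analysis.** Sections 8.1.2 and 8.2.1 specify intention to treat. No planned analysis uses the concomitant medication data.

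**The concern.** Patients dose themselves at home, and the test product can be bought without prescription. As the plan is written, a regular user of fisetin or quercetin supplements can be randomized, and a placebo patient can take either product throughout follow-up without departing from the protocol.

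Use in the placebo arm makes the two arms more alike. Intention to treat rightly keeps such patients where they were randomized, so the estimated effect moves toward no difference and power falls. An analyst cannot reliably repair this later, because the plan neither forbids the use nor asks about it directly. With 75 patients per arm and power set at 80%, there is little reserve to absorb dilution.

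**Working it through.** **1. Inputs.** From Sections 8.1 and 8.2.1: 75 per arm, two-sided 0.05, 80% power, odds ratio (OR) 2.24, ordinal logistic regression on the 7-point score. From the Synopsis and Section 6.2: 20 mg/kg on four dosing days. From Section 1.1 (Investigational Product): 30 capsules of 100 mg per container, under $20. The documents give no rate of non-study use and no distribution over the seven categories. Both are assumed below.

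**2. Reproducing the stated power.** The Whitehead proportional-odds formula is n per arm = 6(z_α/2 + z_β)² / [ln(OR)² (1 − Σp̄³)], where p̄ is the mean category probability over the two arms. Assuming seven equally likely control categories, n = 74.2 per arm, and power at 75 per arm is 80.4%. The stated figure reproduces under that assumption.

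**3. Is copying the study dose feasible?** For an assumed 80 kg patient: 20 × 80 / 100 = 16 capsules a day; 16 × 4 = 64 capsules; 64 / 30 = 2.13, so three containers, under $60. It is affordable, but it takes 16 capsules on each dosing day.

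**4. Dilution when users obtain the full effect.** Let a fraction c of the placebo arm obtain the whole fisetin effect, and let the log odds ratio shrink by (1 − c). Then OR = 2.24^(1−c) and power = Φ(2.802(1 − c) − 1.960), where 2.802 = 1.960 + 0.842.

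- c = 5%: OR 2.15; Φ(0.702) = 76%
- c = 10%: OR 2.07; Φ(0.562) = 71%
- c = 20%: OR 1.91; Φ(0.282) = 61%

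**5. Check by a second method.** Mixing the fisetin-arm distribution into the placebo arm and refitting a common odds ratio (equal control categories) gives 2.15, 2.06 and 1.90, with power 76, 71 and 61%. Restoring 80% power would take 83, 93 and 118 per arm.

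**6. Dilution when users obtain part of the effect.** If each user obtains a quarter of the effect (assumption), replace (1 − c) by (1 − c/4). At c = 10%: 2.802 × 0.975 − 1.960 = 0.772, and Φ(0.772) = 78%.

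**7. Sensitivity to the category distribution.** With 70% of controls in the best category and 15, 5, 4, 3, 2 and 1% in the others (assumed), power is 56% before any non-study use and 48% at 10% use with full effect. The starting level depends heavily on this distribution, but the direction of the loss does not.

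**The case against.** The strongest reply is that the effect may be small and partly visible already.

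- **Dose.** The tested exposure is a 20 mg/kg pulse. One 100 mg capsule in an 80 kg person is 1.25 mg/kg, one-sixteenth of that. No passage says that supplement-level intake has a senolytic effect in humans. This stands, and it makes the full-effect figures the upper end of the loss at each rate of use.
- **Detection.** Medication is reviewed at every contact, and the investigator may exclude any unsuitable candidate. Regular use could therefore come to light. But neither provision restricts use, supplements are not named, and as-needed drugs are exempt from the randomization record.
- **Power base.** The arithmetic uses the ordinal model of Section 8.1, whereas Section 5.1 names a death-or-hospitalization composite and Section 8.2.1 a chi-square test. The percentages do not carry over to that analysis.
- **Text not reproduced.** The label instructions mentioned in Section 6.2 and the consent form might address supplements. The point is limited to the protocol text.

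A reader might also infer more than the documents support:

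- **That no other senolytic is restricted.** Dasatinib falls under the Appendix C holds. The gap is fisetin and quercetin supplements.
- **That the retail and study products are identical.** Only the strength matches. The study capsules come from a contracted GMP manufacturer.
- **That any brief use carries over for weeks.** Section 1.1 (Background) gives 10 days to 6 weeks for senescent cells to recur, but only if the inducers persist, and it claims this at least in vitro.
- **That prior use biases the comparison.** Randomization is expected to balance prior use across the arms. It may reduce the observable effect, but it does not act on one arm only, as placebo-arm use does.

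**Conclusion.** The omission is clear in the text: nothing excludes current or recent users of fisetin or quercetin supplements, nothing bars non-study use, and no direct question measures it. Placebo-arm use would dilute the intention-to-treat comparison.

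The size is unknown because no rate of use is given. At assumed rates of 5, 10 and 20% with full effect, the stated 80% power falls to about 76, 71 and 61%. At 10% use with a quarter of the effect it is about 78%. These figures rest on the ordinal model of Section 8.1 and on shrinkage of the log odds ratio in proportion to use.

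It is tempting to conclude that a null result could not be interpreted. The figures do not support that: at low rates of use the dilution is modest. This is a cheap improvement worth making, not a defect that invalidates the trial.

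**What to change.** 1. **Section 4.2.2 and the Synopsis:** add an exclusion for current or recent use of fisetin or quercetin supplements. The sponsor should set and justify the look-back period; the recurrence time in Section 1.1 (Background) is in vitro support only.
2. **Section 4.3:** state that non-study fisetin and quercetin supplements are not to be taken, at least through the 30-day primary endpoint window and preferably to Day 60, when the long-hauler endpoint is assessed.
3. **Section 3.4 and the visit timetable:** add one direct question on these products at screening and at each scheduled call, and report use by arm. Even without the other two changes, this would show readers how much dilution to allow for.

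Leave prescribed drugs such as dasatinib to the existing Appendix C rules.

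The cost is two lines of protocol text and one question per contact. The downside is the loss of a few candidates who already take these supplements.
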